9.6.1 INTRA-OPERATIVE REMOVAL

Intra-operative removal is the excision of the investigation bioprosthesis before the EDWARDS INTUITY Valve System procedure was completed. The heart was not restarted with the bioprosthesis implanted. During the aortic valve replacement (AVR) procedure, should removal of the bioprosthesis be required after the frame was expanded, use of a nerve hook is recommended. Using a scalpel the operator shall carefully cut the bioprosthesis holder retaining sutures and remove the complete delivery system. Then, insert the nerve hook through the outflow aspect of the bioprosthesis. Operator is to engage the expanded frame with the nerve hook and gently pull the frame inward. Then, operator is to disengage the collapsed portion of the frame inwards. The expanded frame at another location, gently pulling the frame inwards. The expanded frame should be engaged and collapsed at least at 3 radial locations. Once the frame is collapsed, the operator shall cut the nadir sutures and remove the bioprosthesis with forceps.

9.6.2 INTRA-OPERATIVE OR EARLY POST-OPERATIVE EXPLANT

Intra-operative explant is the excision of the investigation bioprosthesis, or part of the investigation bioprosthesis, after the EDWARDS INTUITY Valve System procedure was completed and the heart was restarted with the bioprosthesis implanted. The

¹⁴ Data evaluation to be performed by a Core Lab as described in the Echo Manual.

bioprosthesis is explanted by accessing the aortic valve site and excising the valve as described in section 9.6.1.

This procedure is also recommended in the early AVR post-operative period, before substantial ingrowth tissue has occurred.

9.6.3 LATE POST-OPERATIVE EXPLANT

During the late AVR post-operative period, should explantation of the bioprosthesis be required the device and the surrounding anatomy should be assessed (echo/x-ray or visually) to determine the most appropriate course of action.

The bioprosthesis is designed to allow:

- Collapsing of the frame using a nerve hook.
- Removal of the pericardial leaflets only.
- Separation from the frame by severing the connections between the bioprosthesis wireform and the frame.
- Implantation of a transcatheter valve (Per Instructions For Use in regions where such devices are approved for this intended use)

9.7 MISSED SUBJECT VISITS

The Investigator(s) will make every attempt to follow the subjects and subjects will be encouraged by the Investigator(s) to report any address or telephone number changes to the investigational center. They will also be informed of the importance of returning for scheduled follow-up visits even if they are not having any problems.

If a subject cannot be reached for a follow-up visit, the Investigator will document on the eCRF, the efforts undertaken to contact the subject or the subject's primary health care provider. These efforts should include 3 attempts of telephone contacts at separate dates and times, and a registered letter before the end of the follow-up window. If a subject cannot be reached for the follow-up visit and misses the scheduled visit, the visit will be recorded as a missed visit on the date of last attempted contact. Subjects who miss a visit will not be considered withdrawn. At the next visit interval, the Investigator and/or designee will attempt to contact the subject again for follow-up. Should this attempt to contact the subject fail, a family member should be contacted in addition to the subject. Subjects who miss 2 sequential follow-up visits will be considered lost to follow-up at the second missed visit and exempt from future investigator will attempt to determine if the subject is alive, including searching national mortality registries as permitted by local laws.

9.8 INVESTIGATION SUBJECT EXIT

Investigation Subjects exit the investigation when no additional follow-up visits, procedures, or data collection are required. A subject is exited from the investigation in the following instances:

• Subject fails enrollment criteria after written consent (section 6)

TRITON Surgical Treatment of Aortic Stenosis with a Next Generation Surgical Aortic Valve Clinical Protocol Number: 2009-01

- Subject is excluded intra-operatively by investigator prior to attempted placement of the investigational device (section 6.3)
- Subject is Lost-to-follow-up (section 9.7)
- Subject withdraws from the investigation (section 6.3)
- Subject Death (section 11.3.1)
- Subject completes investigation follow-up (section 9.4.3

9.9 CLINICAL INVESTIGATION TERMINATION

The principal investigator(s) will be notified in writing upon termination of the clinical investigation. The Investigation Sponsor retains the right to suspend or terminate this clinical investigation at any time. Safety review committees associated with the clinical investigation may recommend termination should safety concerns warrant such action. Upon investigation termination, the Investigator will contact the investigation subjects to perform a final follow-up assessment within 2 months of investigation termination. If a subject completed a protocol scheduled clinical evaluation within 6 months prior to investigation termination, the final follow-up assessment may be completed by telephone. Subjects should continue seeing their physicians as part of routine clinical follow-up after heart valve replacement surgery.

10 DATA COLLECTION AND REPORTING

10.1 DATA COLLECTION METHODS

All required data for this investigation are to be collected with standardized Case Report Forms (CRFs) for individual subjects; samples are provided in Section 17.8. Electronic CRFs (eCRFs) will be utilized for this investigation. eCRFs must be electronically signed by the Principal Investigator or co-Investigator listed in the Clinical Studies Agreement and Delegation of Authority Log. If for any reason the eCRFs are unavailable and/or inaccessible, paper CRFs will be provided by the Investigation Sponsor to be completed, signed by the Principal Investigator or designee and submitted to the Investigation Sponsor.

Primary data collection should be drawn from hospital chart and operator worksheet (source document) reviews. eCRFs must be kept current to reflect subject status during the course of the investigation.

Case Report Form Instructions will be provided to assist the Investigator(s) and appropriate investigation staff in the completion of the required eCRFs.

10.2 SOURCE DOCUMENTATION REQUIREMENTS

Regulations require that Investigators maintain information in the clinical investigation subject's medical records that corroborate data collected on the eCRFs. In order to comply with these regulatory requirements, the following information will be maintained as required by the Investigation Sponsor monitors and/or regulatory inspectors:

- 1. Medical history and physical condition of the clinical investigation subject before involvement in the clinical investigation sufficient to verify protocol entry criteria
- 2. Dated and signed notes in the subject's medical record on the day of entry into the clinical investigation.
- 3. Dated and signed notes, laboratory records, and test reports, from each clinical investigation subject visit with reference to the eCRFs for further information, if appropriate (for specific results of procedures and exams).
- 4. Notations on abnormal lab results and adverse events reported and their resolution.
- 5. Notes regarding concomitant anticoagulant/antithrombotic medications taken during the clinical investigation
- 6. Subject's condition upon completion of or withdrawal from the clinical investigation.

10.3 QUALITY CONTROL AND QUALITY ASSURANCE PROCEDURES

Because of the potential for errors or inaccuracies in entering data into eCRFs, originals or photocopies of all relevant procedural records and reports, post-procedural examinations, laboratory and other test results may be kept on file in the Investigator's subject files. eCRFs and copies of test results must be available at all times for inspection by the investigation monitor.

Data Management personnel will employ a full-featured relational Oracle database application on a central server. The application provides the capability of data collection remotely through the Internet so the participating site personnel may log on the system securely and enter the data. Other data management programming and/or data analyses will be done in the database system through the sponsor's internal network. All subjects' data collected in the system will be extensively verified through data validation programs, database integrity rules, and investigation-specific data entry conventions for data accuracy and logical meaningfulness. Periodic analysis of all subjects' collected data will be performed in order to examine the expected distributions of data and to identify outliers for possible data entry errors.

11 REPORTABLE EVENTS / EFFECTS

Reportable event codes are provided in the eCRF synopsis for this investigation.

11.1 REPORTING PROCEDURE

Adverse event information will be reported throughout the clinical investigation as they occur. Adverse events will be followed until they are adequately resolved or explained. The investigator(s) will report any serious adverse event to the Investigation Sponsor's Clinical Research department no later than three calendar days after the Investigators first learns of the event, followed by relevant source documents in ten working days. It is preferable for the investigator to notify the Investigation Sponsor's Clinical Research department within 24 hours of occurrence or knowledge of the device related event. Notification should be done via email to [contact] or faxed to [contact]. In addition, investigational centers will report all serious adverse events to their local EC and National Competent Authority in accordance with the review committee's and national requirements.

11.2 DEFINITIONS

For purposes of this protocol adverse event definitions are taken from the guidance ISO document; please refer to ISO 14155:2011.

11.2.1 Adverse event

An adverse event (AE) is defined as any untoward medical occurrence, unintended disease or injury, or untoward clinical signs (including abnormal laboratory findings) in subjects, users or other persons, whether or not related to the investigational medical device.

NOTE 1: This definition includes events related to the investigational medical device or the comparator.

NOTE 2: This definition includes events related to the procedures involved.

NOTE 3: For users or other persons, this definition is restricted to events related to investigational medical devices.

11.2.2 Adverse device effect

An adverse device effect (ADE) is defined as any adverse event related to the use of an investigational medical device.

NOTE 1: This definition includes adverse events resulting from insufficient or inadequate instructions for use, deployment, implantation, installation, or operation, or any malfunction of the investigational medical device.

NOTE 2: This definition includes any event resulting from use error or from intentional misuse of the investigational medical device .

11.2.3 SERIOUS ADVERSE EVENT

A serious adverse event (SAE) is defined an adverse event that:

a. led to death,

b. led to a serious deterioration in the health of the subject, that either resulted in:

- 1. a life-threatening illness or injury, or
- 2. a permanent impairment of a body structure or a body function, or
- 3. in-patient or prolonged hospitalization, or
- 4. medical or surgical intervention to prevent life-threatening illness or injury or permanent impairment to body structure or a body function,

c. led to fetal distress, fetal death or a congenital abnormality or birth defect.

NOTE: Planned hospitalization for a pre-existing condition, or a procedure required by the CIP, without serious deterioration in health, is not considered a serious adverse event.

11.2.4 SERIOUS ADVERSE DEVICE EFFECT

A serious adverse device effect (SADE) is defined as an adverse device effect that results in any of the consequences characteristics of a serious adverse event.

11.2.5 UNANTICIPATED SERIOUS ADVERSE DEVICE EFFECT (USADE)

Serious Adverse Device Effect which by its nature, incidence, severity or outcome, has not been identified in the current version of the risk analysis.

Note: Anticipated serious device effect (ASADE) is an effect which by its nature, incidence, severity or outcome has been identified in the risk analysis report.

11.3 DEATHS AND EXPLANTS

11.3.1 SUBJECT DEATHS

In the event of subject death, every effort should be made to obtain a copy of the death certificate, the autopsy report and/or the death summary. Information on the cause of death and its relationship to the device used in this clinical investigation will be determined by the principal investigator. Copies of an autopsy report, if available, and/or a death summary are to be sent to the Investigation Sponsor.

If a device is explanted during autopsy, the device should be returned to the Investigation Sponsor for analysis. Return kits for devices will be provided upon request by the clinical monitor.

11.3.2 DEVICE EXPLANTS

In the event a bioprosthesis is explanted in the intra-operative or early post-operative period (i.e., while the subject is hospitalized at the investigational center), a copy of the procedure report must be provided to the Investigation Sponsor. Information on the cause of explant and its relationship to the bioprosthesis will be determined by the principal investigator. Explanted bioprostheses during this period must be returned to the Investigation Sponsor for analysis. Return kits for devices will be provided upon request by the clinical monitor.

In the event a bioprosthesis is explanted in the late post-operative period, every effort should be made to obtain a copy of the explant procedure report, as applicable. Information on the cause of explant and its relationship to the bioprosthesis will be determined by the principal investigator. Copies of an explant report, if available, are

to be sent to the Investigation Sponsor. Explanted bioprostheses during this period should be returned to the Investigation Sponsor for analysis. Return kits for devices will be provided upon request by the clinical monitor.

12 STATISTICAL ANALYSIS

12.1 SAMPLE SIZE PHASE I

The Phase I investigation will enroll 10 subjects for feasibility. No statistical justification is established.

12.2 SAMPLE SIZE PHASE II

Phase II will enroll up to 340 subjects. The sample size is determined based on ISO5840 requirements. The rational for the increase is based on estimation of the number of additional subjects required in order to reach a minimum of eight subjects implanted with the smallest valve size tested (19 mm valves) and a minimum of fifteen subjects implanted with the larger 27mm valve size tested to met ISO5840 requirements.

12.3 PHASE I ANALYSIS

Phase I consists of the first 10 subjects enrolled to the investigation.

The following primary safety endpoints will be summarized by counts and percentages based on 30-day follow-up:

- study valve-related mortality,
- thromboembolic events,
- study valve thrombosis,
- major bleeding events,
- study valve paravalvular leakage, and
- study valve endocarditis.

In addition, the following safety endpoints will also be summarized by counts and percentages based on 30-day follow-up:

- all-cause mortality,
- study valve structural valve deterioration,
- hemolysis,
- study valve-related reoperation,
- study valve explantation, and
- all adverse events.

12.4 PHASE II ANALYSIS

12.4.1 ANALYSIS POPULATION

The primary safety analysis will include all the enrolled subjects including those enrolled in Phase I. The performance analysis will include the subjects who survived at least 30 days post implant.

12.4.2 SAFETY ANALYSIS

For reporting purposes, the percent of subjects who experience an early adverse event within 30 days of implant for the events listed in the primary safety endpoints will be summarized. Linearized rates will be used to summarize adverse events for the late (>30 days) post-operative period for the events listed in the primary safety endpoints. The linearized rates will be reported as the number of events occurring after the early post-operative period per year of subject survival.

Actuarial analysis according to Kaplan-Meier will be used to estimate probability of freedom from each adverse event listed in the primary safety endpoint.

The percentages for the early events and linearized rates for the late events will also be calculated for the other complications.

Blood data (red blood count, white blood count, hematocrit, hemoglobin, platelet count, serum lactate dehydrogenase, haptoglobin, and reticulocytes) will be collected preoperatively, at 6-months, 1-years, and 5-years post implant. Data will be reported as the percent of subjects with results within the normal ranges at each time interval.

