9.2.2 EDWARDS INTUITY AORTIC VALVE IMPLANTING PROCEDURE

A detailed description of device preparation and use is provided in the Instructions for Use (IFU) of both Models 8300ACA and 8300ACB, (See Clinical Investigator's Brochure). Investigators must be familiar with Precautions and Technique information described in the IFU prior to use of the bioprosthesis and the delivery system. The EDWARDS INTUITY Valve System implanting procedure uses one bioprosthesis and one delivery system. A second attempt, with new devices, is permitted. If the second attempt is not successful, no further attempts are permitted and the subject should be treated with another surgical valve.

A Transesophageal echo (TEE) should be performed after the bioprosthesis is implanted to assess placement, potential paravalvular leak, and mitral valve function.

Procedural information, findings, results and device identification information to be recorded is identified in Table 2.

⁹ Data evaluation to be performed by a Core Lab as described in the Echo Manual.

General information	Clinical information	Device performance
Date of Admission Date of Procedure Implanting Surgeon Type of Operation	Etiology Diagnosis for replacement Valve implantation Condition of the native aortic valve Sizing Concomitant procedures Intraoperative Adverse Events	Bioprosthesis size and serial number Delivery system size, lot, and components used Device technical success

Table 2: Procedural information

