9.3 SUBJECT ENROLLMENT

Subjects will be considered enrolled into the clinical investigation after meeting all the enrollment criteria, signing the informed consent, and after the surgeon sizes the aortic annulus, and determines that the bioprosthesis can be implanted. The point of enrollment in Phase I and Phase II of the clinical investigation is established in the Operating Room when the investigator sizes the aortic annulus and confirms that the subject is an appropriate candidate for the investigation device(s)¹⁰. All subjects enrolled in this clinical investigation must be followed as described in section 9.4 and section 9.5

Adverse events are collected from the time the subject provides consent.

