12.4.3 PERFORMANCE ANALYSIS

The device technical success and procedure success will be summarized by counts and percentages.

Subjects will be analyzed according to the NYHA classification preoperatively, at 3 months and annually post implant for 5 years. The distribution (numbers of subjects and percentages) in the various NYHA classes will be tabulated at each follow-up interval.

Echocardiography data will be obtained preoperatively, at discharge (or 10-days post implant, whichever occurs first), at 6-months and at 1, 3, and 5 year follow-ups. Descriptive statistics for the continuous echo variables and change from baseline (e.g. mean, standard deviation, and range) will be categorized by time interval and size. Regurgitation data will be summarized using frequency at each severity level.

Improvement in regurgitation at one year will be analyzed via the Wilcoxon Signed-Rank test. Change at one year from baseline for all other hemodynamic outcomes will be analyzed using paired *t*-tests.

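### The 30-day post-implant survivor restriction can drop failed deliveries from device technical success, and the early-event window has no defined day 0 for subjects who never receive a study valve

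*Combined protocol and SAP*

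**What the plan says.** - **Who is enrolled.** Section 9.3 fixes enrollment in the operating room, at annulus sizing. Its footnote requires the devices to be used; it does not require an implant to be achieved. Section 9.2.2 allows a second attempt with new devices and then says: "If the second attempt is not successful, no further attempts are permitted and the subject should be treated with another surgical valve".
- **Who stays in.** Section 9.3 adds: "All subjects enrolled in this clinical investigation must be followed as described in section 9.4 and section 9.5". Section 9.6 keeps subjects with device removal in follow-up. Section 9.8 lists exclusion before attempted placement as an exit reason; a failed attempt is not listed.
- **Populations (12.4.1).** For safety: "The primary safety analysis will include all the enrolled subjects including those enrolled in Phase I". For performance: "The performance analysis will include the subjects who survived at least 30 days post implant".
- **Success endpoints.** Section 5.2 defines device technical success as one valve delivered and deployed with one delivery system, and procedure success as technical success without certain later events, death among them. Section 12.4.3 says: "The device technical success and procedure success will be summarized by counts and percentages". It gives no separate population.
- **Event windows (12.4.2).** Phase II early events are "the percent of subjects who experience an early adverse event within 30 days of implant". For late events: "Linearized rates will be used to summarize adverse events for the late (>30 days) post-operative period". For Phase I, 12.3 says: "The following primary safety endpoints will be summarized by counts and percentages based on 30-day follow-up".

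**The concern.** A subject who leaves the operating room with another surgical valve after two failed attempts is the clearest possible failure of delivery. That subject is enrolled, followed and counted in the safety population, but has no study-valve implant date. The performance population is defined by survival from implant, so on its literal wording it leaves this subject out of the one endpoint that measures delivery.

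Section 2.2 gives the short-term safety and performance of device deployment and delivery as part of the study's purpose, in support of a CE marking application. A technical success rate computed without the failed deliveries would not answer that question.

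The early safety percentage raises a lesser problem of the same kind. Its denominator is all enrolled subjects, but its window starts at an event that some of them never had.

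**Working it through.** **Plan's own figure.** 10 subjects in Phase I (12.1) + 340 in Phase II (12.2) = 350, which matches section 4.2. This is the planned safety denominator. The documents give no failed-attempt rate and no expected event rates, so every rate below is an assumption except the 2 to 8% operative mortality quoted in 3.3.

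**Step 1: technical success.** Let N = 350, k = subjects never implanted, s = subjects implanted at the second attempt (failures by definition, because more than one valve and delivery system were used), and d = deaths within 30 days, taken to fall among first-attempt successes.

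- Over all enrolled: (N − k − s)/N.
- Over 30-day survivors post implant, read literally: (N − k − d − s)/(N − k − d).

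| k | s | d | All enrolled | Population of 12.4.1 |
|---|---|---|---|---|
| 14 | 10 | 0 | 326/350 = 93.1% | 326/336 = 97.0% |
| 14 | 10 | 7 (2% of 336) | 326/350 = 93.1% | 319/329 = 97.0% |
| 14 | 10 | 27 (8% of 336) | 326/350 = 93.1% | 299/309 = 96.8% |
| 4 | 0 | 0 | 346/350 = 98.9% | 346/346 = 100% |
| 35 | 0 | 0 | 315/350 = 90.0% | 315/315 = 100% |

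With s = 0 the second formula equals 1 whatever k is. Second-attempt implants who survive 30 days remain in the population as failures, so the result is 100% by construction only when every failure is a never-implanted subject. Under these assumptions, early deaths hardly change the contrast.

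**Step 2: if implant is read as the procedure.** Never-implanted subjects who live 30 days then come back in, but anyone who dies within 30 days is still out. Procedure success is judged at discharge or day 10, whichever comes first (5.2). Any death that counts as a failure there therefore falls inside the 30 days that remove the subject, and the death component can never register. For technical success, the effect of dropping deaths depends on whether they fall among successes or failures.

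**Step 3: early percentage.** Let p = early risk in implanted subjects and q = early risk in never-implanted subjects, for an event that can occur without a study valve.

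- Literal implant anchor: (N − k)p/N.
- Anchored at the index procedure: [(N − k)p + kq]/N.

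With k = 18 (18/350 = 5.1%) and p = 3%, 332 × 0.03 = 9.96 events among the implanted.

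- Literal: 9.96/350 = 2.85%.
- Procedure, q = 5%: (9.96 + 0.90)/350 = 3.10%.
- Procedure, q = 20%: (9.96 + 3.60)/350 = 3.87%.

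At k = 4 and q = 20%, the figures are 10.38/350 = 2.97% against 11.18/350 = 3.19%. At k = 35 and q = 20%, they are 9.45/350 = 2.70% against 16.45/350 = 4.70%.

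These figures apply to one event type at a time, because the plan specifies no pooled early rate.

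**The case against.** A reader might infer that early events are counted only from a study-valve implant, so that a failed-attempt subject can never contribute a safety event. The documents do not support that.

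- Implant is not defined as a clock origin. The nearest definition, a footnote to exclusion criterion 11 in 6.2.2, explains what previously implanted means and serves eligibility.
- Elsewhere the protocol treats implant and procedure as the same date. Section 5.2 counts ten days from implant, and 9.4.2 counts the same ten days from the procedure.
- Section 12.4.2 goes on to call its own early window a post-operative period. Late events use post-operative wording, Kaplan-Meier has no stated origin, Phase I uses 30-day follow-up, and adverse events are collected from consent (9.3).

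This part of the objection stands: the loss of early events is one literal reading of an undefined term, and it affects one of several summaries. What remains is that day 0 is unsettled and could be chosen after the data are seen.

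On technical success, it can be said that the endpoint is assessed at the procedure and recorded in Table 2, so the data exist. That is true, but 12.4.1 and 12.4.3 still name only the survivor population for analysing it.

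It is also fair that these are descriptive figures. No test or performance goal is set on them, and 2.2.1 makes success a judgement of the data monitoring committee on 3-month data. If failed attempts are rare, the bias is small.

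**Conclusion.** The point on the performance population holds. Read literally, 12.4.1 removes from device technical success the subjects who failed it most completely, which favours the device. Read as the procedure date, it still removes 30-day deaths, and with them every death that procedure success is meant to count. The illustrative gap is 93.1% against 97.0%, on assumed counts of 14 never implanted and 10 second-attempt implants with no early deaths. The true gap depends on a failure rate that the documents do not give.

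The point on the early percentage holds only as an ambiguity. On the literal reading, early thromboembolic events, major bleeds and deaths in never-implanted subjects are missing from the numerator while those subjects stay in the denominator. At about 5% failed and 3% risk in the rest, the shortfall runs from 0.25 percentage points (q = 5%) to about 1 point (q = 20%). A large fixed understatement of the early rate is not established, because it would rest on assumed risks.

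Study valve thrombosis, paravalvular leakage and study-valve endocarditis cannot practically arise without a study valve. For these, the denominator matters whatever clock is used.

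**What to change.** - **12.4.1 and 12.4.3:** compute device technical success and procedure success over all enrolled subjects in whom an attempt was made, without the 30-day survival restriction.
- **12.4.2:** define day 0 as the date of the index procedure, for early events, late events and Kaplan-Meier, in all enrolled subjects whatever valve was finally placed.
- **12.4.2:** report study valve thrombosis, paravalvular leakage and study-valve endocarditis also over subjects who received a study valve. Moving day 0 alone would leave never-implanted subjects diluting these rates.

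The cost is a few sentences in section 12 and slightly more analysis. The procedure date and technical success are already collected (Table 2), and no treatment or follow-up rule changes. The reported rates may look less favourable.

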9.4.2 DISCHARGE

A clinical evaluation of Phase I or Phase II subjects, including an echocardiogram (refer to Section 9.5), will be performed at the time of hospital discharge. Medical information, findings, and results to be recorded are identified in Table 3.

¹⁰ The bioprosthesis and the delivery system must be used.

General information	Clinical information	Echocardiography ¹¹
Date of Discharge	Weight	Date of exam
	Heart rate	2D measurements
	Cardiac Rhythm (12-lead EKG)	Ejection fraction
	Anti-thromboembolic therapy	Aortic bioprosthesis assessment
	Adverse Events	LVOT assessment
	Coagulation Profile	Mitral Valve assessment
		Other Variables
		Left Ventricular Assessment

Table 3: Discharge Evaluation

Subjects, who are not discharged within 10 days post procedure must have an echocardiogram (refer to Section 9.5) to further assess placement and performance of the bioprosthesis. This echocardiogram is required to complete the evaluation of procedural success. Those subjects will not require an additional echocardiogram at discharge.

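### Late linearized rates for study-valve events are divided by survival time that can include time without the study valve

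*Combined protocol and SAP*

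**What the plan says.** All places are in the combined protocol and SAP.

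- Section 12.4.2: "Linearized rates will be used to summarize adverse events for the late (>30 days) post-operative period". The rate is reported as "the number of events occurring after the early post-operative period per year of subject survival". This covers the primary safety endpoints. The same section adds that "linearized rates for the late events will also be calculated for the other complications", which brings in structural valve deterioration, reoperation and explant.
- Section 12.4.1: "The primary safety analysis will include all the enrolled subjects including those enrolled in Phase I".
- Section 9.3 places enrollment at annulus sizing. Footnote 10, attached to that section, adds: "The bioprosthesis and the delivery system must be used". Use does not mean that the valve stays in. Under section 9.2.2, if a second attempt fails, "the subject should be treated with another surgical valve".
- Section 9.3 also says: "All subjects enrolled in this clinical investigation must be followed as described in section 9.4 and section 9.5". Section 9.6 keeps subjects with removal or explant in follow-up, without routine echocardiography or blood tests after discharge. Section 9.8 does not list removal or explant as a reason for exit.
- Section 12.4.2 also plans Kaplan-Meier estimates for the primary safety endpoints. It gives no censoring rule for them.

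**The concern.** A subject who no longer carries the study valve, or never left surgery with it, cannot have a new late thrombosis, paravalvular leak, endocarditis or structural deterioration of that valve. Such a subject adds years to the denominator and nothing to the numerator. For these endpoints the rate can only fall, so the error runs in the device's favour.

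These rates, with the Kaplan-Meier curves, are the planned late summary of primary safety. Section 2.2 says that the results will support a CE Marking application and describes long-term outcomes in relation to marketed bioprostheses. Because the plan does not say how time without the valve is handled, two analysts could report different rates from the same data.

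**Working it through.** The plan states no expected rate, event count or person-year total, so there is no figure to reproduce. What can be checked is how the denominator scales.

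**Inputs from the documents.** 350 subjects (10 + 340), 5 years of follow-up each (section 4.2), late period after day 30 (section 12.4.2).

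**Assumptions.** The share of enrolled subjects who leave surgery without the study valve is *e* = 0 to 5%. The explant hazard is *x* = 0 to 1% per year. There are no deaths or early exits, except in the mortality check below.

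**Scaling.** Reported rate ÷ rate per valve-year = late valve-years ÷ late survival-years. The understatement is therefore the share of late survival time spent without the valve.

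**Late survival-years.** Per subject: 5 − 30/365 = 4.918 years. Total: 350 × 4.918 = 1,721.2.

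**Late valve-years.** 350 × (1 − *e*) × ∫ exp(−*x*t) dt, from t = 30/365 to 5.

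| *e* | *x* per year | Valve-years | Understatement at 5 years |
|---|---|---|---|
| 0 | 0 | 1,721.2 | 0% |
| 1% | 0 | 1,704.0 | 1.0% |
| 0 | 1% | 1,678.2 | 1 − 1,678.2/1,721.2 = 2.5% |
| 5% | 1% | 1,594.3 | 1 − 1,594.3/1,721.2 = 7.4% |

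**At 1 year.** *e* = 1% with *x* = 0 gives 1.0%; *e* = 5% with *x* = 1% gives 5.5%.

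**Mortality check.** With an assumed 5% per year mortality in both terms, *x* = 1% alone gives 1 − 1,483.2/1,519.7 = 2.4%. The last row becomes 1 − 1,409.0/1,519.7 = 7.3%. Mortality hardly matters.

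**Against sampling error.** Assume 20 late valve events. The plan's denominator gives 20/1,721.2 = 1.16 per 100 years, with an exact Poisson 95% interval of 0.71 to 1.79. The largest scenario gives 20/1,594.3 = 1.25, well inside that interval.

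**Loss to follow-up.** Section 9.7 dates loss at the second missed visit and asks for a search for vital status, including mortality registries. No passage says that analysis time ends at last contact.

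- A subject last seen at year 1, 2 or 3 is classed as lost 24 months later. If that time counted, each 1% of subjects so lost would add 1% × 2/4.918 = 0.41% to the denominator.
- A subject last seen at year 4 who misses year 5 is not treated as withdrawn and could add up to about 12 months: 1% × 1/4.918 = 0.20% per 1% of subjects.
- If registry survival were counted, 0.41% would not be a ceiling.

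**The case against.** The strongest reply is that little turns on this. The rates are descriptive. Section 2.2.1 makes Phase II success a Data Monitoring Committee judgement on 3-month data. No test, target rate or sample size uses the late rates. All of that stands.

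It can also be said that section 12.4.1 fixes a population, not a clock. The early period is defined for subjects "who experience an early adverse event within 30 days of implant", which gives no date to someone who left surgery without the valve, so leaving them out is a possible reading. That is fair. On that reading, the explant part alone remains: 0 to 2.5% at 5 years under the assumptions above.

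Three stronger readings are tempting, and the documents do not support them.

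- *The denominator has no start or stop at all.* Survival ends at death, the late period is given as beyond 30 days, and section 9.8 lists the exits. Counting from implant would lower all late rates by a further 30/1,825 = 1.6% at 5 years or 30/365 = 8.2% at 1 year, but the wording points to late survival. What is missing is a stop at removal or explant for valve-specific events, and a rule on last contact.
- *Subjects with a failed attempt cannot have a valve-related death, so they should leave that rate too.* Section 3.1 lists injuries from the frame and delivery system and says that such risks may lead to death. Section 11.3.1 relates a death to the device used, not to a device still in place. Removing these subjects could drop device-related deaths.
- *All late rates are biased in the same way.* Thromboembolism, major bleeding, hemolysis and all-cause mortality do not need the study valve to be in place.

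**Conclusion.** The point holds for the valve-specific endpoints. Taken literally, the plan's denominator includes time without the study valve, the direction favours the device, and no other section corrects it.

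The size is unknown from 0% upward, because the documents give no failed-implant, explant or loss rate. The 0 to 7.4% range at 5 years rests wholly on the assumed 0 to 5% without the valve and 0 to 1% per year explanted. That the effect is small is a judgement drawn from those assumptions, not a figure in the plan. A reader should not infer that any conclusion on safety would be reversed. This is a cheap improvement.

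**What to change.** Add to section 12.4.2:

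(a) Late person-time runs from day 31 after the index procedure to the earliest of death, withdrawal, last contact with known event status, or data cut-off. Survival learned only from a mortality registry counts for all-cause mortality only.

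(b) For study valve thrombosis, paravalvular leakage, study valve endocarditis, structural valve deterioration, explant and study valve-related reoperation, person-time also ends at complete removal or explant. The explant or reoperation itself counts as an event. Subjects who leave surgery without the study valve contribute no late time. Section 9.6.2 lets an explant be partial, so one line should say how a partial explant is counted.

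(c) For study valve-related mortality, thromboembolism, major bleeding, hemolysis and all-cause mortality, all enrolled subjects, including failed attempts, stay in both numerator and denominator. The hemolysis table should note that routine blood tests stop after discharge in subjects with removal or explant (section 9.6).

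(d) Kaplan-Meier censoring uses the same end dates. The rate per all-enrolled survival time is reported as a sensitivity analysis.

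The cost is a few sentences and some programming, using procedure, visit, explant and death dates that the study should already hold. The downside is that the affected rates rise slightly and denominators differ by endpoint, so each table must show its own.
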